3.5 General statistical analysis guidelines

The analyses will be conducted in the entire population. The denominator for all data will be the total number of women randomized to each group. Two-sided p-values less than 0.05 will be considered statistically significant.

Normality of continuous variables will be assessed using the Shapiro-Wilkes test and a visual inspection of the data distribution. Continuous variables that are normally distributed will be reported as means \pm standard deviation. Non-normally distributed data will be reported as median and interquartile range (25th and 75th percentile). Categorical variables may be collapsed as necessary depending on data distribution, although all efforts will be made to maintain pre-determined categories. Categorical variables will be presented as n (%).

Data will be examined descriptively. Crude proportions of the primary and secondary outcomes at 8 weeks will be reported. Log-binomial regression will be used to calculate risk ratios and 95% confidence intervals (CIs) to assess whether the intervention was efficacious. We will assess each portion of efficacy separately (improvement and distress) as well as combined. If differences between the intervention and control groups as seen as baseline, these may be adjusted for in a log-binomial regression.

Chi-square or Fisher's exact tests may be used to calculate p-values to assess differences between categorical variables, as appropriate based on distribution of the data. To assess differences in normally distributed continuous variables between groups, the Student's T-test will be used to calculate p-values. To assess differences in non-normally distributed continuous variables between groups, the Wilcoxon rank-sum test will be used. Log-binomial regression will be used to calculate risk ratios and 95% CIs to assess the association between the intervention and all categorical variables. Linear regression will be used to calculate difference in means and 95% CI to assess the relationship between the intervention and all continuous variables.

In the event that the log-binomial regression does not converge, modified Poisson regression with robust standard errors will be substituted. If this is consistent problem, the statistician may decide to use this approach for all calculations of risk ratios and 95% CIs.

Due to the nature of the pilot/feasibility study, results of the primary analysis should be reported with caution. The initial sample size and follow up time was not achieved.

4. Additional comments

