NCT 03632447

A Prospective Randomized Efficacy Study Comparing a Pelvic Digital Health System Home Program of Pelvic Floor Muscle Exercise to Kegel Exercises in the Treatment of Stress-Predominant Urinary Incontinence

Statistical Analysis Plan

August 27, 2019

Statistical Analysis Plan

Secondary analysis of a Prospective, Nested, Randomized Efficacy Study Comparing a Pelvic Digital Health System Home Program of Pelvic Floor Muscle Exercise to Kegel Exercises in the Treatment of Stress-Predominant Urinary Incontinence (Renovia-05) –
Pilot/Feasibility Trail

Principal Investigator: Renovia Inc.

Prepared by: [name]

August 12, 2019

Table of Contents

1. Objectives.....	3
2. Design.....	3
3. Statistical analysis	3
3.1 Participant description.....	3
3.2 Feasibility	3
3.2.1 Feasibility of randomization.....	3
3.2.2. Feasibility of digital health platform	3
3.3 Compliance	4
3.4 8-week assessment	4
3.5 General statistical analysis guidelines.....	5
4. Additional comments.....	6
4.1 Reporting of statistical analyses	6
4.2 Additional analyses	6

1. Objectives

- Assess the feasibility of a randomized trial to test the efficacy of using a novel intravaginal system (leva[®] Plus Pelvic Digital Health System) to perform pelvic floor muscle exercises (PFME) compared to a Kegel exercise home program in women with stress-predominant urinary incontinence (SUI)
- Assess any technical issues with the digital aspect of the leva[®] Plus Pelvic Digital Health System
- Evaluate compliance with exercises in the leva[®] Plus Pelvic Digital Health System arm of the study

2. Design

The initial randomized study was ended early due to technical difficulties. This will be analyzed as a pilot/feasibility trial. Details about the randomized controlled trial study design and study visits can be found in the protocol, Renovia-05 (Sponsor: Renovia Inc.)

The study enrolled 60 women, randomized into the two initial arms (30 women per arm) and followed participants for 8 weeks.

3. Statistical analysis

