- **Pelvic Floor Disability Index (PFDI):** Obtain the mean value of all of the answered items within the corresponding scale (possible value 0 to 4) and then multiply by 25 to obtain the scale score (range 0 to 100). Missing items are dealt with by using the mean from answered items only. For the summary score, add the scores from the 3 scales together to obtain the summary score

(range 0 to 300). This can be reported as a continuous variable or may be categorized depending on distribution of the data. For the primary outcome, “No urinary distress” will be defined as a raw score of 2 or less on all six indicators in the UDI-6 subscale. Raw scores of greater than 2 will be considered reports of distress.

- **Pelvic Organ Prolapse/Urinary Incontinence Sexual Questionnaire (PISQ-IR):** Validated scoring available from Constantine, M.L., Pauls, R.N., Rogers, R.R. et al. *Int Urogynecol J* (2017) 28: 1901.
- **McGill Pain Questionnaire:** The level of pain for each word can be reported as None, Mild, Moderate, Severe. Collapsing of responses is also possible (pain vs. no pain, no/mild pain vs. moderate/severe pain). Reporting of the visual analogue scale will depend on data recording. Reports of pain location will need to be manually reviewed and categorized.
- **Self-Efficacy Scale for Practicing Pelvic Floor Exercises (SESPPFE):** Sum all of the scores to calculate total score for the scale. This can be reported as a continuous variable or may be categorized depending on distribution of the data.
- **Patient Global Impression of Improvement (PGI-I) Scale:** This is only a single question and will be dichotomized as improvement (“very much better” or “much better”) vs. no improvement (all other non-missing answers).
- **Patient Global Impression of Severity (PGI-S) Scale:** This is only a single question and can be reported as is.
- **World Health Organization Disability Assessment Schedule (WHODAS):** Two options are available for scoring the WHODAS. The first is a simple summary score as a continuous variable. The second option is to use the available coding provided by the WHO (http://apps.who.int/iris/bitstream/handle/10665/43974/9789241547598_eng.pdf;jsessionid=680B7F5F1FC5DE085FA4DCFD302F1176?sequence=1). A score of 17 or greater constitutes significant disability.

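### SAP 3.5 divides every categorical outcome by all women randomised, so missing week-8 values lower the printed percentage in unfavourable categories and distort the arm comparison if loss is unequal

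*SAP*

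**What the plan says.** SAP 3.5 sets the analysis set and the denominator in two sentences: "The analyses will be conducted in the entire population" and "The denominator for all data will be the total number of women randomized to each group". No outcome is excepted. The same section presents categorical variables as counts with percentages and then says: "Log-binomial regression will be used to calculate risk ratios and 95% CIs to assess the association between the intervention and all categorical variables".

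Several measures in SAP 3.4 can be printed as unfavourable states:

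- McGill pain words are graded from none to severe and may be collapsed to any pain or to moderate/severe pain.
- WHODAS may be a continuous score, but a cut-off is also given: "A score of 17 or greater constitutes significant disability".
- PGI-S: "This is only a single question and can be reported as is".
- POP-Q may be split at stage II.

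The only missing-data rule is at item level, for the PFDI and PFIQ, where the mean of the answered items is used. The SAP has no rule for a woman with no week-8 data, no missing category in the tables and no sensitivity analysis for missing outcomes. For the PGI-I, SAP 3.4 counts as not improved only those women who gave some other answer, which leaves out women with no answer.

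**The concern.** One denominator rule acts in opposite directions depending on how the outcome is worded. For improvement on the PGI-I, counting a missing woman as not a success works against the arm with more loss. For moderate or severe pain, the same arithmetic works in favour of that arm, because a woman who is not assessed can never add to the count of women affected.

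The pilot will be read mainly through its percentages. If loss differs between arms, a table of pain, severity or disability could show a difference that comes only from attendance at week 8.

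The rule can also reach a primary outcome. SAP 3.4 defines the second efficacy outcome as the absence of urinary distress, but SAP 3.5 calls that component distress. If it were modelled as distress present, with the all-randomised denominator, women with no data would count as not distressed.

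**Working it through.** **Inputs.** SAP section 2 gives the size: "The study enrolled 60 women, randomized into the two initial arms (30 women per arm) and followed participants for 8 weeks". So N = 30 per arm. The denominator rule is from SAP 3.5. Week-8 loss by arm is not given, so the losses below are assumptions. The only attrition figure in the documents is about 15%, in Protocol 10.1.1, for the trial as first planned. The plan gives no figure of its own on this point.

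**Formula.** Let x be the number of women observed in the unfavourable state, n the number with a week-8 value, and m = 1 - n/N the missing fraction.

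- Printed percentage = x/N = (x/n) × (n/N) = observed rate × (1 - m).
- Ratio of printed percentages, leva to Kegel = (ratio of observed rates) × (1 - m in leva)/(1 - m in Kegel).

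**Equal observed rates, so the ratio should be 1.00:**

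| Lost, leva v Kegel (of 30 each) | Calculation | Printed ratio |
|---|---|---|
| 3 v 3 | 27/27 | 1.00 |
| 6 v 3 | 24/27 | 0.89 |
| 7 v 2 (9/60 = 15% overall) | 23/28 | 0.82 |
| 9 v 3 | 21/27 | 0.78 |
| 9 v 0 | 21/30 | 0.70 |
| 3 v 9 | 27/21 | 1.29 |

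With equal loss the ratio is right, but both percentages are too low. At 15% loss each is 0.85 of the observed rate.

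**A worked table, assuming 9 v 3 lost and one third of observed women affected in each arm:**

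- Observed denominators: 7/21 (33.3%) v 9/27 (33.3%), risk ratio 1.00 (95% CI 0.45 to 2.24).
- SAP denominators: 7/30 (23.3%) v 9/30 (30.0%), risk ratio 0.78 (0.33 to 1.82). A log-binomial fit gives the same values.
- In the leva arm, affected plus not affected is 7/30 + 14/30 = 21/30 = 70%, not 100%.
- Stated as free of the problem, the same data give 14/30 v 18/30, also a ratio of 0.78, but now against leva.

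**Reversal with the same losses.** Observed 9/21 (42.9%) v 10/27 (37.0%), ratio 1.16, leva worse. Over 30 per arm it becomes 30.0% v 33.3%, ratio 0.90, leva better.

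**The regression.** If missing is coded 0 so that the model follows the stated denominator, the worked table gives 0.78. If missing records are dropped, the model gives 1.00, beside printed percentages of 23.3% and 30.0%. The SAP does not say which applies.

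**The PGI-I.** Under SAP 3.4, improved plus not improved adds up to the women who answered. Under SAP 3.5 the denominator is 30. With any missing answer the two cannot both be followed without a third category, and none is defined.

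**The case against.** The strongest reply is that SAP 3.5 fixes a denominator and does not recode anyone. Nowhere does the SAP say that a woman without data is free of the problem, and the PGI-I wording suggests that missing women are not moved into the opposite category. If all pain grades are printed, the rows will add to less than 100% and the gap will be visible. This stands in part: the effect comes from the rule and is not a stated assumption. But the gap disappears from view when only one side of a dichotomy is printed, and the risk ratio remains undefined.

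The second reply concerns scope, and it stands. A reader might infer from the wording of the rule that every outcome is affected. Means, medians, t-tests, rank-sum tests and linear regression use observed values. WHODAS can be reported as a continuous score, and the McGill and POP-Q dichotomies are optional.

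The third concerns direction. A reader might infer that the rule favours leva, because the trial stopped early for technical reasons and Protocol 8.3.3 lists inability to use the device as a ground for withdrawal. These make unequal loss plausible but do not show it. No loss by arm is reported, and more loss in the Kegel arm would push the ratio the other way.

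The fourth concerns importance. It is tempting to call pain the trial's tolerability measure. The Protocol synopsis lists the McGill questionnaire under efficacy, and places adverse events under safety and tolerability. The intervals at 30 per arm are also wide, and the SAP already asks for cautious reporting. General caution does not, however, correct a percentage computed on the wrong denominator.

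**Conclusion.** The point holds for categorical outcomes printed as unfavourable states. Followed as written, SAP 3.5 understates each such percentage by the missing fraction. It also multiplies the between-arm ratio by the ratio of the retained fractions. Under the losses assumed above with leva losing more, a true ratio of 1.00 is shown as 0.89 to 0.70; with the 9 v 3 loss exchanged between arms it is shown as 1.29. The size and direction in this trial are unknown. Risk ratios share the bias only if missing is coded 0; otherwise they disagree with the printed percentages whenever loss is unequal. The conflict between SAP 3.4 and 3.5 on missing PGI-I answers is in the text and needs no assumption about which arm lost more. The documents do not support a claim that all outcomes are biased, or that leva is the arm favoured.

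**What to change.** In SAP 3.5:

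1. Keep the all-randomised denominator, with missing counted as not a success, only for PGI-I improvement, no urinary distress and the two combined. State that these are always modelled as success. Change the PGI-I wording in SAP 3.4 to agree.
2. For all other categorical outcomes, use women with a week-8 value as the denominator for both percentages and risk ratios, and print the number missing by arm.

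Optionally, add a worst-case line for pain and disability that counts missing women as affected. In the worked table it would give (7 + 9)/30 = 53.3% v (9 + 3)/30 = 40.0%, a ratio of 1.33. Observed denominators can themselves mislead if the women lost differ from those seen, and this line shows how far that could go. In a stopped pilot it is a matter of choice.

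The cost is a short SAP edit and one extra table row per outcome. Percentages for unfavourable states will be higher, by a factor of 1/(1 - missing fraction).

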- At 6- and 12- months they will participate in validated questionnaires (see chart) by phone and email or mail, in addition to reporting what (if any) additional therapies they have undergone for treatment of stress urinary incontinence at 6 months and 12 months after baseline.
- The third party research center will provide a single phone call to the subjects receiving the leva plus to ensure the device is functioning properly. If there are questions regarding the device function, a conference call will be undertaken to allow the subject to trouble-shoot device function with the sponsor technical specialist. The sponsor will at no time possess protected health information (PHI)

VISIT CONTENT

At week 4 all study participants will return to the office to undergo a PFDx evaluation of pelvic floor muscle function and complete and return the following questionnaires:

- a. PFDI
- b. PISQ-IR
- c. McGill Pain Questionnaire
- d. SESPPFE
- e. Patient Global Impression of Severity and improvement (PGI-S, PGI-I) Scale
- f. WHODAS
- g. PFIQ

At week 8 all study participants in both arms will return to the clinic for the PFDx device evaluation of pelvic floor muscle function and physical examination including a POP-Q and Brinks score, and the following questionnaires:

- a) PFDI
- b) PISQ-IR
- c) McGill Pain Questionnaire
- d) SESPPFE

- e) PGI-S and PGI-I
- f) WHODAS
- g) PFIQ
- h) Attestation of 80% or greater compliance with exercises twice daily as per protocol

The 6 and 12 months follow-up by phone and email or mail will include:

- i) PFDI
- j) PISQ-IR
- k) McGill Pain Questionnaire
- l) SESPPFE
- m) PGI-S and PGI-I
- n) WHODAS
- o) PFIQ

PFDx device pelvic floor muscle evaluation for both study arms will include:

- Baseline pelvic floor muscle vaginal angle (at rest)
- Pelvic floor muscle vaginal angle with Valsalva
- Pelvic floor muscle angle with relaxation
- Pelvic floor muscle angle with muscle contraction
- Number of repetitions of contraction in 15 seconds;
- Maximum time a subject can sustain a pelvic floor muscle contraction.

This evaluation will be conducted using the PFDx device placed in the vagina by the subject and conducted by study staff using an automated measurement protocol.

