10.1.1 Determination of Sample Size

This planned randomized controlled trial is a tertiary prevention trial, comparing the efficacy of the Leva device in the treatment of stress urinary incontinence to standard pelvic floor muscle training, consisting of office education and a home exercise program. Our primary outcome is the proportion of subjects who are very much better/much better as measured by the PGI-I. Sample size for 20% difference between groups given a 30% success rate of home exercise programs, $\alpha=0.05$, and a power of 0.8, the needed sample size is 93 patients in each arm. Allowing for an attrition rate of approximately 15%, we require approximately 225 patients.

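### Week-4 scores are collected for PFDx and eight questionnaires but never analysed, so women with no week-8 value drop out of the continuous comparisons

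*SAP*

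**What the plan says.** Protocol 8.1 schedules a full assessment of both arms halfway through treatment: "At week 4 all study participants will return to the office to undergo a PFDx evaluation of pelvic floor muscle function and complete" the PFDI, PISQ-IR, McGill, SESPPFE, PGI-S, PGI-I, WHODAS and PFIQ. The flow chart in Protocol section 4 agrees. The Brink score, POP-Q, voiding diary and CGI are not scheduled at week 4.

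The SAP does not mention week 4. SAP 3.4 places both definitions of efficacy at the 8-week visit, and SAP 3.5 says "Crude proportions of the primary and secondary outcomes at 8 weeks will be reported". Continuous outcomes get a t-test or rank-sum test, and "Linear regression will be used to calculate difference in means and 95% CI to assess the relationship between the intervention and all continuous variables". Baseline adjustment is mentioned only for log-binomial regression. The significance rule is "Two-sided p-values less than 0.05 will be considered statistically significant".

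On missing data, SAP 3.4 covers unanswered items within the PFDI and PFIQ. Nothing covers a missed visit. SAP 3.5 makes the number randomized to each arm the denominator for all data.

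**The concern.** A mean or regression on week-8 values cannot have every randomized woman as its denominator unless missing values are filled in, and the SAP gives no way to do that. The stated principle is all-randomized, but for continuous outcomes the stated methods give a completers' analysis. A woman seen at week 4 and not at week 8 contributes nothing, although her week-4 score says a good deal about how she was doing.

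Loss that differs by arm is conceivable. Only the leva arm depends on a device and app, SAP section 2 says the trial ended early for technical difficulties, and Protocol 10.1.1 planned for attrition of about 15%. If leva women doing poorly at week 4 leave and comparable controls stay, a completers' comparison flatters leva.

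**Working it through.** **The plan's own figure.** Protocol 10.1.1: "Sample size for 20% difference between groups given a 30% success rate of home exercise programs", two-sided 0.05, "and a power of 0.8, the needed sample size is 93 patients in each arm". With pooled variance, n = [1.96·√(2·0.4·0.6) + 0.842·√(0.3·0.7 + 0.5·0.5)]² / 0.20² = (1.358 + 0.571)² / 0.04 ≈ 93 per arm, which matches. For attrition, "Allowing for an attrition rate of approximately 15%, we require approximately 225 patients": 186 / 0.85 = 219, close to 225. These figures are not in dispute. They supply the 15%, which is a planning value for the full trial and not an observed loss.

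**Inputs for the check.** From SAP section 2: 30 women per arm. Assumed: 15% loss at week 8 in each arm, everyone seen at week 4, and a true difference of 0.50 SD on a score where higher is better. Base correlations, also assumed: 0.6 (baseline–week 4), 0.5 (baseline–week 8), 0.75 (week 4–week 8).

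**Selective pattern.** In the leva arm, 27% of the worse half at week 4 leave and 3% of the better half (average 15%); control loss is random. The mean of a half-normal is √(2/π) = 0.798, so among leva women who stay the week-4 mean shifts up by

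0.798 × (0.97 − 0.73) / (0.97 + 0.73) = 0.113 SD.

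Unadjusted week-8 bias = 0.113 × (week 4–week 8 correlation):
- correlation 0.4: 0.045 SD
- correlation 0.5: 0.056 SD
- correlation 0.75: 0.084 SD
- correlation 0.85: 0.096 SD

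Baseline-adjusted bias ≈ 0.113 × (r48 − r08·r04):
- base case: 0.113 × (0.75 − 0.30) = 0.051 SD
- correlations 0.5, 0.4 and 0.5: 0.113 × (0.50 − 0.20) = 0.034 SD
- r48 = 0.85: 0.062 to 0.073 SD, depending on the baseline correlations

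**Simulation at 30 per arm, base correlations (true value 0.50):**

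| Loss pattern | Completers, unadjusted | Completers, baseline-adjusted | Using week 4 |
|---|---|---|---|
| Random | 0.50 | 0.50 | 0.50 |
| Poor responders, leva only | 0.58–0.59 | 0.55–0.56 | 0.50 |
| Poor responders, controls only | 0.42 | 0.45 | 0.50 |
| Poor responders, both arms | 0.50 | 0.50 | 0.50 |

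**Steeper selection.** With leva-only dropout following a logistic curve in the week-4 score (assumed slope 1.5 log-odds per SD) and correlations 0.4 to 0.8, unadjusted bias is 0.05–0.10 SD at 10% loss, 0.07–0.14 at 15% and 0.11–0.22 at 25%. With no true effect and 15% loss, the t-test rejects 5.6%, 6.8% and 8.0% of the time at correlations 0.4, 0.6 and 0.8, against a nominal 5%. Using week 4 brings the bias to about zero.

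**Precision under random loss.** Base case: the standard error falls from 0.249 to 0.240 (about 4%), with 0.228 for complete data. In variance terms, (0.0620 − 0.0576) / (0.0620 − 0.0520) = 44% of the lost precision is recovered. With a week 4–week 8 correlation of 0.5 it falls from 0.261 to 0.258 (about 1%). If half of those lost leave before week 4, base correlations give 0.246 to 0.242 (about 2%).

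**Scale.** At 15% loss, 25.5 women per arm remain, so the unadjusted standard error is √(2/25.5) = 0.28 SD.

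**The case against.** Three stronger readings are tempting, and the documents support none of them.

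- *A reader might infer that every outcome has a week-4 value.* The Brink score, POP-Q, voiding diary and CGI do not, so a week-4 model cannot be fitted directly to them.
- *A reader might infer that selective loss has biased the comparison.* No document gives loss between weeks 4 and 8, overall or by arm. SAP section 2 says the study ended early for technical difficulties, not that women left because of them. Bias needs loss that is both outcome-related and different between arms, and it could go against leva.
- *A reader might infer that the primary outcomes are exposed in the same way.* Both are binary, and an all-randomized denominator amounts to counting missing women as non-successes. The SAP's PGI-I scoring note limits non-improvement to non-missing answers, which sits badly with that rule but is a separate inconsistency. The gap is mainly in the continuous secondary measures.

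It is also fair to say that the effect is small. The base-case adjusted bias of 0.05 SD is about a fifth of its standard error, and the completers' 95% interval still covered the truth 94.5% of the time. The SAP's objectives are feasibility, technical issues and compliance, it asks for cautious reporting, and SAP 3.2.1 requires participant flow to be shown.

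That lowers the priority without removing the point. The SAP still tests at two-sided 0.05, its stated continuous analyses are unadjusted and so carry the larger bias, and cautious wording does not correct an estimate.

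**Conclusion.** The point holds for outcomes measured at both visits. The SAP leaves the week-4 data unused, and its continuous methods cannot honour its own denominator.

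At an assumed 15% loss, with all women seen at week 4 and poor responders leaving the leva arm only, the bias towards leva is about 0.03–0.07 SD baseline-adjusted and 0.05–0.14 SD unadjusted. The precision gain is about 1–4% of the standard error at week 4–week 8 correlations of 0.5 to 0.75, and less if some women leave before week 4. Loss rates, correlations and dropout patterns are all assumptions. The bias is a risk to guard against, not a demonstrated result. Given the 60-woman pilot, this lies between an optional and a recommended change.

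**What to change.** In SAP 3.4 and 3.5:

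1. For PFDI, PFIQ, PISQ-IR, SESPPFE, WHODAS and the PFDx measures, estimate the week-8 difference with a repeated-measures mixed model: arm by visit, baseline value, unstructured covariance, and every woman with a week-4 or week-8 value. Keep the rank-sum test as a supportive analysis where the distribution is clearly non-normal.
2. For PGI-I and UDI-6 success, keep the all-randomized denominator and say outright that a missing week-8 status counts as non-success. Add a sensitivity analysis that multiply imputes it by arm from the week-4 response.
3. Report the number with a missing week-8 value by arm for every outcome, including the Brink score, POP-Q and voiding diary, which have no week-4 value to draw on.

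The cost is more analysis code and no new data. The model assumes that loss depends on observed values. A woman with neither a week-4 nor a week-8 value still contributes nothing to the model, so the denominator statement for continuous outcomes should be reworded to say who is included.

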8 INVESTIGATIONAL PLAN

8.1 Overall Study Design and Plan

- A prospective, nested, randomized multicenter controlled study to evaluate the efficacy of using the leva® Plus Digital Pelvic System to perform PFME in comparison to Kegel exercises.
- Subjects will be patients referred to a Urogynecologist's office for evaluation.
- Following completion of baseline screening and consent, patients will be randomized by study coordinators at the baseline office visit using an automated randomization system.
- Patient population: women with moderate to severe SUI or stress-dominant mixed urinary incontinence.
- The duration of participation is 8- weeks, with expected post-intervention follow up surveys 6- and 12-months after study terminus.
- Up to 75 participants per site will be enrolled for a total of 225 subjects in the trial.

STUDY ENROLLMENT

The women interested in the study will be screened for participation based on inclusion/exclusion criteria and the MESA questionnaire identifying stress or stress-dominant mixed incontinence, and the UDI-6 (score > 25).

Screening visit: The study will be explained by the study staff and the consent will be reviewed with prospective participants.

- 1) The following questionnaires will be administered:
 - a. MESA
 - b. UDI-6
- 2) Pelvic exam will be performed including:
 - a. POP-Q (acceptable to report from an exam within 3 months of baseline)
 - b. Pelvic floor muscle assessment (Brink Scale) (may be performed at baseline or screening visit (if screening < 3 months prior to baseline)
- 3) If the eligibility requirements are met, patients should be given a 3-day voiding diary (acceptable if reported within 3 months of baseline visit)

The consent will be obtained by the licensed physician investigators or study assistants. Study participation will be entirely voluntary.

STUDY PROCEDURES

Once patients have undergone the appropriate screening evaluation, met criteria for study participation, and provided informed consent, subjects will be randomized to one of two study arms. The "Kegel" arm will involve patient education and performance of Kegel exercises, the current standard of care. The "Leva" arm of the study will undergo patient education and performance of pelvic floor muscle exercises using the Leva system. Subjects in the "Leva" arm will be sub-randomized to one of two long term follow up plans, follow up without reminders or follow up using automated reminders by text message.

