3.1 Participant description

Baseline characteristics will include demographics (i.e. participant age, race, other measures of SES) and medical history (i.e. gravidity, parity, history of abdominal surgery) as reported on the baseline questionnaires. In addition, the results of the initial exam assessing urinary incontinence (including voiding diary, Pelvic Organ Prolapse assessment (POP-Q), PFDx device assessment) and the results of the questionnaires administered (PFDI, PISQ-IR, McGill Pain Questionnaire, SESPPFE, PGI-S, PGI-I, WHODAS, PFIQ) will be reported for both groups. Available scoring for all validated measures will be used.

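### SAP 3.5 lets chance baseline differences decide whether and how the efficacy risk ratios are adjusted, and does not say which estimate is primary

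*SAP*

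**What the plan says.** SAP section 3.5 sets the main efficacy analysis: "Log-binomial regression will be used to calculate risk ratios and 95% confidence intervals (CIs) to assess whether the intervention was efficacious". No covariates are named. Each of the two efficacy definitions (PGI-I improvement and absence of urinary distress) is to be analysed alone and combined. The adjustment rule follows: "If differences between the intervention and control groups as seen as baseline, these may be adjusted for in a log-binomial regression". The only threshold in the section is general: "Two-sided p-values less than 0.05 will be considered statistically significant". Nothing ties it to the baseline comparison.

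SAP section 3.1 lists the variables that could trigger the rule. The list is open: "Baseline characteristics will include demographics (i.e. participant age, race, other measures of SES) and medical history (i.e. gravidity, parity, history of abdominal surgery"; the examination, "including voiding diary, Pelvic Organ Prolapse assessment (POP-Q), PFDx device assessment"; and the questionnaires, "PFDI, PISQ-IR, McGill Pain Questionnaire, SESPPFE, PGI-S, PGI-I, WHODAS, PFIQ) will be reported for both groups".

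The trial's size is in SAP section 2: "The study enrolled 60 women, randomized into the two initial arms (30 women per arm". The closing caution of section 3.5 asks for restraint in reporting, because the planned size and follow-up were not reached. It does not choose a model.

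**The concern.** In a randomised comparison, a baseline difference between arms is a chance event. Its size says nothing about whether the variable predicts outcome. A rule driven by observed imbalance can therefore bring in covariates that carry no information and leave out a strong predictor that happens to be balanced. Baseline symptom severity is the obvious candidate. UDI-6 is an entry criterion (Protocol 8.3.1), and the PFDI that contains it is completed at the baseline visit (Protocol 8.1), yet the SAP never names it as a covariate.

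Because adjustment is optional and no estimate is called primary, each primary outcome can end with a crude risk ratio and one or more adjusted ones. The SAP is dated after the study had stopped enrolling, so its wording is the main safeguard against a choice made once both results are known.

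**Working it through.** **1. The plan's own figure.** The documents give no probability of a chance baseline difference. Their only design calculation is the sample size in Protocol 10.1.1 (30% v 50%, two-sided 0.05, power 0.80):

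n = [1.96·√(2·0.4·0.6) + 0.8416·√(0.3·0.7 + 0.5·0.5)]² / 0.2² = (1.358 + 0.571)² / 0.04 = 93 per arm.

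This reproduces. Allowing 15% attrition, 186/0.85 = 219, close to the stated 225 or so. At 30 per arm the power is 35%. None of this settles the present point, but it sets the scale.

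**2. Number of candidate variables (SAP 3.1).** Demographics and history 6 (SES counted once), examination 3, questionnaires 8 at total-score level: 6 + 3 + 8 = 17. Splitting PFDx into the five measures in SAP 3.4 gives 17 − 1 + 5 = 21.

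**3. Chance that at least one differs at p<0.05.** If independent, 1 − 0.95^k: k = 17 gives 58.2%, k = 21 gives 65.9%. Simulated t-tests, 30 per arm, with a common correlation:

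| Correlation | 0 | 0.1 | 0.2 | 0.3 | 0.5 |
|---|---|---|---|---|---|
| k = 17 | 58% | 57% | 54% | 49% | 39% |
| k = 21 | 66% | 64% | 61% | 55% | 43% |

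The documents do not give the correlation, so the range is about 40-66%. Two qualifications:
- Fisher's exact test is conservative at 30 v 30 (true size 0.9-2.7%). With 5 of 21 variables tested at 2% each, 1 − 0.95^16 × 0.98^5 = 60%.
- If a difference means a standardised difference above 0.25, its standard error is √(2/30) = 0.258. Each variable then exceeds the limit by chance about 33% of the time, and 1 − 0.667^17 is over 99%.

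The expected number selected at p<0.05 is 21 × 0.05 = 1.05, so usually one variable enters.

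**4. Effect on the answer.** Simulated trials of 30 per arm used modified Poisson with robust standard errors, with covariates chosen by t-test p<0.05. Four variables were prognostic. In A, C and D the coefficients on the logit scale were 0.8 per SD for severity and 0.4 for three others; in B all four were 0.35. A has 20 variables, the others 21. A and C take success of roughly 30-50%. D sets the arms at 30% v 50% overall. B was run under the null only. Trials per scenario: A 6,000, B 3,000, C 4,000, D 4,000.

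| Set, correlation | Null rejection: crude / rule / better of two | Power: crude / rule / fixed severity | Disagree on significance, true effect |
|---|---|---|---|
| A, 0 | 4.1 / 4.7 / 5.8% | 34 / 31 / 34% | 10% |
| B, 0 | 3.8 / 4.0 / 5.2% | not run | not run |
| B, 0.2 | 3.2 / 4.1 / 5.2% | not run | not run |
| C, 0 | 3.6 / 4.2 / 5.4% | 37 / 34 / 37% | 9% |
| C, 0.3 | better of two 6.6% | not tabulated | 17% |
| D, 0 | 3.6 / 4.3 / 5.3% | 32 / 28 / 34% | 10% |
| D, 0.3 | 3.0 / 4.3 / 5.8% | 31 / 30 / 36% | 16% |
| D, 0.5 | 3.2 / 4.4 / 6.2% | 32 / 31 / 38% | 17% |

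Correlation lowers the trigger rate but makes the choice of model matter more. In C the two analyses disagreed in 14% of triggered trials at correlation 0 and 30% at 0.3; at 0.3 the typical shift in the risk ratio, where triggered, was a factor of about 1.2.

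**The case against.** The best defence is that a default can be read in the text. Section 3.5 gives an unadjusted log-binomial risk ratio first and mentions adjustment afterwards as an option. The aims are feasibility, technical issues and compliance, and the SAP itself urges caution. That reading is natural, and it limits the practical consequence. But the SAP never says so. It keeps two outcomes labelled primary and a 0.05 threshold, so the ambiguity stands.

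A reader might also infer more than the documents support:
- *That chance triggers the rule in about two thirds of trials.* This needs about 21 independent variables, each tested at 0.05. No test is named as the trigger, related questionnaires are unlikely to be independent, and 21 is reached only by splitting PFDx. One of the 17, PGI-I, is missing from the baseline questionnaires in Protocol 8.1, although the flow chart shows it.
- *That the rule seriously inflates false positives.* Under the rule alone, rejection stays below 5%. Even reporting the better result gives no more than 6.6%.
- *That the model is likely not to converge.* The SAP already provides a modified Poisson fallback, and non-convergence of the log-binomial model was not tested here. Usually only about one covariate would enter.
- *That site should be added where numbers permit.* The statement "Up to 75 participants per site will be enrolled for a total of 225 subjects in the trial" describes the planned trial. The SAP does not say how the 60 women were spread over sites, and a site term conditional on numbers would be another data-dependent rule.

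**Conclusion.** The point holds as a defect of specification with modest numerical effect. Adjustment is triggered by chance, is optional, and leaves the primary risk ratio for each efficacy outcome open. If a difference means p<0.05 on 17 to 21 variables, the trigger rate is about 40-66%; under a looser reading it approaches certainty. The crude and rule-adjusted results disagreed on significance in about 9-17% of simulated trials with a true effect. The power cost against a fixed model is about 3 points in two simulations and about 6 when the arms are set at exactly 30% v 50%, in a trial with only about 35% power in any case.

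These sizes rest on assumed correlations (0 to 0.5) and assumed prognostic strength. The documents do not say how well baseline UDI-6 predicts either outcome, and the entry limit of 25 narrows its range. The precision gain from fixed adjustment may therefore be small: the SD of the log risk ratio fell by 4% in set A. The real gain is one analysis defined in advance.

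**What to change.** Replace the conditional sentence in SAP 3.5 with:

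> The primary model for each efficacy outcome adjusts for the continuous baseline UDI-6 score (from the PFDI completed at the baseline visit), whatever the observed balance; the unadjusted risk ratio is shown beside it. Baseline differences are described and do not change the model.

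Naming the baseline-visit PFDI as the source matters because UDI-6 is also taken at screening. Keep the existing modified Poisson fallback. Add no site term that depends on the numbers found.

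The chance that baseline data alter the primary model then falls to zero. Declaring the unadjusted risk ratio primary and deleting the conditional sentence would also remove the ambiguity, but would forgo whatever precision baseline severity offers. The cost is a short replacement in the SAP, no new data, and the loss of the freedom to adjust after seeing the results.
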